The **P**otassium Intake-response **T**rial to **C**ontrol **H**ypertension (**PITCH**) will test the intake-response relationship between potassium supplementation and BP, which may (1) inform clinical guidelines on the optimal level of potassium supplementation for BP lowering among adults with elevated BP and hypertension and dietary guidelines for population intake and (2) lay the foundation for further investigations, including mechanistic studies and outcome trials. A large meta-analysis of RCTs identified a dose-response relationship between BP lowering and risk of CVD, with a 5 mm Hg reduction in systolic BP reducing major CVD events by 10%.⁸ Modeling studies suggest that as little as a one mm Hg reduction in the mean systolic BP in the US population would reduce >20,000 coronary heart disease, stroke, and heart failure events annually.^{30,31}

Our long-term goal is to establish effective, scalable, and sustainable nonpharmacological

interventions, like potassium supplementation, for primary prevention of CVD. The specific goal of PITCH is to study the intake-response effect for 4 levels of potassium supplementation on 24-hour systolic BP among adults with untreated elevated BP or hypertension. We will test the following hypotheses:

Primary hypothesis: Compared with placebo (0 mmol/day potassium supplementation), there is a progressive, linear dose-response relationship between increasing doses of oral potassium supplementation (30, 60, and 90 mmol/day or 1173, 2346, 3519 mg/day) and decreasing levels of 24-hour systolic BP from baseline to 12-weeks of follow-up, and the largest BP lowering effect will be observed with a dose of 90 mmol/day (3519 mg/day).

Secondary hypotheses: Potassium supplementation improves levels of 24-hour diastolic BP, and office, daytime, and nighttime systolic and diastolic BP, and these improvements are greater with increasing potassium intake.

Exploratory hypotheses: We will examine the effects of potassium supplementation on other CVD risk factors, such as sodium excretion, and study the mediating effects of potassium-induced changes in CVD risk factors on BP. In addition, we will explore treatment effects by subgroups, including age, sex, race, baseline BP, central adiposity, and baseline sodium and potassium intake.

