Throughout the entire investigation, strict quality assurance (QA) and quality control (QC) measures will be used. This section describes some of the approaches.

Manual of Procedures: We will develop a study protocol and detailed manual of procedures (MOP) that identifies and details standard procedures for all elements of data collection in the trial. The MOP will be adapted from MOPs used successfully in previous RCTs conducted within the Office of Health Research

Training and Certification: Office of Health Research personnel will be trained based on established and effective methods. Training will focus on core trial elements, such as recruitment, retention, intervention, blinding, and data completeness and quality. Periodic re-training/certification sessions will be conducted to ensure all trial-related procedures are being applied in a standard manner across all participants. Throughout the trial, the investigators will monitor every aspect of study performance throughout the trial to make sure that the objectives are met, that study visits are timely and comprehensive, and that data are complete and of high quality. The accuracy of all laboratory measures, particularly crucial exposure, outcome, and intervention monitoring variables, will be carefully scrutinized.

3G. Statistical Design and Power

The trial is designed to detect a 1.5 mm Hg reduction in 24-hour systolic BP for each additional 30 mmol/day supplemental potassium compared with placebo, assuming 60 mmol/day achieves a 3 mm Hg reduction based on meta-analyses.^{25–29,34,35,49} We calculated our sample size assuming: 90% statistical power; a 2-sided significance level of 0.05; and a standard deviation of 7 mm Hg in 24-hour systolic BP change based on prior BP RCT experience in this population.^{50,51} The sample size calculation assumes analysis using a 4-group dose-response contrast test and the estimated sample size for each group based on these assumptions is 47. To allow for an 85% follow-up rate, we will recruit 56 trial participants in each group for a total of 224.

3H. Data Management

All study data will be double-entered. The study coordinator will conduct quality control checks on all study forms, study measures, and laboratory data. Data will be cleaned and logically checked and entered into a secure REDCap database.

3I. Statistical Analysis Plan

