Intention-to-treat analyses will be conducted such that the primary and secondary study outcomes will be evaluated among participants according to their randomization assignment at study entry.

Preliminary Data Analysis: Baseline participant characteristics will be summarized as the mean \pm standard deviation or median (interquartile range) for continuous variables and number (%) for categorical variables. Intervention groups will be compared on baseline characteristics to identify possible baseline imbalances.

Analyses of Main Effects: In the analysis of the primary and secondary outcomes, we will test the hypothesis that increasing doses of supplemental potassium result in monotonically greater reductions in levels of outcomes from baseline to 12 weeks follow-up in an intake-response

fashion. To test this hypothesis, we will use linear regression and the F-test of the hypothesis that there is a linear trend in mean net response in outcomes across the 4 randomized groups over 12 weeks. Rejection of the null hypothesis ($\mu_0 = \mu_{30} = \mu_{60} = \mu_{90}$) indicates that there is a significant intake-response relationship (i.e., $\mu_0 \leq \mu_{30} \leq \mu_{60} \leq \mu_{90}$ and $\mu_0 < \mu_{90}$) where the net effects will be calculated as mean changes in outcomes from baseline to 12 weeks follow-up in the potassium supplementation groups minus mean change in outcomes in the placebo group). The linear contrast will be tested using contrast coefficients of -3, -1, 1, 3. This approach is standard for dose-response RCTs.^{52–54} The optimal dose will be defined as that which shows the greatest net decrease in systolic BP over 12 weeks compared with placebo.

Based on a prior meta-analysis, the intake-response shape of potassium supplementation on systolic BP is uncertain.²⁸ The proposed trial is designed to evaluate a linear intake-response effect but will have sufficient power to characterize other possible relationships, including threshold effects, using contrast structures like modified linear, quadratic, exponential, and sigmoid.^{52–54}

In additional analyses, we will use linear mixed effects regression models incorporating follow-up outcome measures at both weeks 6 and 12, and will conduct pairwise comparisons between randomized groups in an exploratory analysis.

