Missing Data and Covariable Adjustment: In the primary analyses, we will use Markov-chain Monte Carlo methods to impute missing values assuming an arbitrary missing pattern and a multivariate normal distribution for the data.^{55,56} We will compare point estimates and confidence intervals from this analysis with a secondary analysis using available data without imputation. In this proposed RCT, we expect baseline characteristics to be balanced between intervention groups. Therefore, in the primary analysis, we will include the stratified randomization variable (i.e., race) as a covariable, but other covariable adjustments will not be used. However, if imbalances are detected, we will adjust for these covariables in secondary multivariable-adjusted regression models.

Analyses of Effect Modification and Mediation: We will evaluate the consistency of intervention effects by age, sex, race, baseline BP, central adiposity, and baseline sodium and potassium intake in stratified analyses. Effect modification will be tested using intervention arm * subgroup interaction terms in regression models. Mediation analysis will be used to evaluate potential mechanisms of potassium supplementation on outcomes. We will compare changes in covariables that could be impacted by the intervention, such as urinary excretion of sodium and potassium, and use structural equation modelling (SEM). SEM allows for simultaneously modelling both indirect and direct effects; i.e., effects of the intervention on the mediator, effects of the mediator on the outcome, as well as the direct effects of the intervention on the outcome (e.g., systolic BP).⁵⁷

The proposed trial is designed to test one primary hypothesis and the other analyses will be considered hypothesis generating. Therefore, a significance level of 0.05 without adjustment for multiple comparisons will be used in analyses of secondary outcomes, subgroups, and effect mediation and modification.

4. Risks

4A. Description of Potential Risks

Risks associated with potassium supplementation, venipuncture, and collection of confidential medical information are the main risks associated with this study.

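### A significant linear trend confirms at most that 90 mmol/day differs from placebo, and only if the response is monotone; dose tests in a fixed order behind it would cost no alpha

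*Combined protocol and SAP*

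**What the plan says.** Under Analyses of Main Effects, section 3I tests a linear trend in change in 24-hour systolic BP with coefficients -3, -1, 1, 3. It reads rejection as ordered means with placebo different from 90 mmol/day. It also states that the shape of the response is uncertain and that threshold effects are possible. The optimal dose is to be the one with the greatest net decrease against placebo, with no test attached.

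On individual doses, the same section says that the investigators "will conduct pairwise comparisons between randomized groups in an exploratory analysis". The end of 3I adds: "The proposed trial is designed to test one primary hypothesis and the other analyses will be considered hypothesis generating". The sentence there on unadjusted testing at 0.05 covers secondary outcomes, subgroups, mediation and modification. No testing order or gatekeeping for the dose comparisons is given.

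The opening statement of aims says the trial may "inform clinical guidelines on the optimal level of potassium supplementation for BP lowering".

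**The concern.** The intended use is dose-specific, while the confirmatory inference is a single slope. A linear contrast combines all four means, so it can be significant without the 90 mmol/day mean differing from placebo. Going from a significant contrast to a statement about 90 mmol/day needs monotonicity, which the plan assumes and does not test. Even with monotonicity, nothing confirmatory follows for 60 or 30 mmol/day.

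The doses have a natural order and the primary test is a single test. A fixed sequence behind it could therefore give dose-specific confirmation without touching the primary analysis. As written, the plan forgoes this, and any statement on an individual dose would rest on exploratory p-values.

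**Working it through.** **Inputs.** From section 3G: "The trial is designed to detect a 1.5 mm Hg reduction in 24-hour systolic BP for each additional 30 mmol/day supplemental potassium compared with placebo", so changes relative to placebo of -1.5, -3.0 and -4.5 mm Hg; "a standard deviation of 7 mm Hg in 24-hour systolic BP change"; "a 2-sided significance level of 0.05"; 47 evaluable and 56 enrolled per arm. From 3I: coefficients -3, -1, 1, 3, with sum of squares 20. From 3B: equal allocation.

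**The plan's own sample size.** Section 3G says "We calculated our sample size assuming: 90% statistical power" and "The sample size calculation assumes analysis using a 4-group dose-response contrast test".

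- Contrast value: (-1)(-1.5) + (1)(-3.0) + (3)(-4.5) = 1.5 - 3.0 - 13.5 = -15.
- Normal approximation: n = 20 × 49 × 10.507 / 225 = 45.8, so 46 per arm.
- The exact noncentral F gives power 0.898 at 46 and 0.905 at 47, so 47 is the smallest n reaching 90%.
- 47 / 0.85 = 55.3, so 56 per arm and 224 in total. The stated figures reproduce.

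**The trend test without monotonicity.** Take an illustrative pattern in which only 60 mmol/day is active, at -9 mm Hg. The contrast is (1)(-9) = -9. The standardised value is 9 × √47 / √(20 × 49) = 61.70 / 31.30 = 1.97, which is the two-sided critical value. The trend is therefore significant in about 50% of trials although 90 mmol/day has no effect. In a fixed sequence the 90 mmol/day test would then pass in 2.5%.

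**Single comparisons with placebo, 47 per arm.** The standard error is 7 × √(2/47) = 1.444 mm Hg.

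| Dose (mmol/day) | Effect / SE | Power, normal | Power, pooled t |
|---|---|---|---|
| 90 | 4.5 / 1.444 = 3.12 | 87.6% | 87.3% |
| 60 | 3.0 / 1.444 = 2.08 | 54.7% | 54.3% |
| 30 | 1.5 / 1.444 = 1.04 | 17.9% | 17.8% |

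**The fixed sequence** (trend, then 90, 60 and 30 against placebo, each two-sided at 0.05, stopping at the first non-rejection). Any false rejection requires rejecting the first true null in the order, which has probability at most 0.05, so the family-wise error is controlled. Simulation of 1,000,000 trials per scenario with pooled variance gives:

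| Design values | Trend | 90 confirmed | 60 confirmed | 30 confirmed |
|---|---|---|---|---|
| 47 evaluable per arm | 90.5% | 86.1% | 51.6% | 14.5% |
| 56 evaluable per arm | 94.6% | 91.6% | 59.9% | 17.5% |

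At 47 per arm, 90 mmol/day is confirmed in 86.1 / 90.5 = 95% of trials with a significant trend.

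**False dose findings when both approaches require a significant trend** (at least one, either direction, 47 per arm):

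| Truth | Unadjusted, after a significant trend | Fixed sequence |
|---|---|---|
| No dose works | 4.0% | 3.5% |
| Only 90 works (-4.5 mm Hg) | 6.6% | 3.2% |

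With no dose working, the family-wise error of the sequence is 5.0% once the trend test itself is counted.

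**The case against.** The strongest reply is that 3I already draws the conclusion about 90 mmol/day from the trend. Under the monotone hypothesis that the plan sets out to test, that inference is valid. This stands. A reader might infer that a positive trial could confirm no dose at all; the documents do not support that for 90 mmol/day unless monotonicity is set aside.

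A second reply is that calling the comparisons exploratory is an honest way to avoid a multiplicity problem. This also stands. A reader might be struck that three unadjusted comparisons, with no gate, give at least one false result in about 12.5% of trials when no dose works, against 3.5% in the sequence. That sets ungated tests against gated ones, for results the plan does not present as confirmatory. With the gate applied to both, the difference is 4.0% against 3.5%. The gain in error control is small there and clearer when only 90 works.

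A third reply is that the fixed order pays off mainly when the response is monotone. With an illustrative peak at 60 (0, -2, -4.5, -2 mm Hg), 60 mmol/day alone has 87% power, but the sequence confirms it in 27% of trials. With -3 mm Hg at every dose, 90 is confirmed in 47% and 30 in 27%. These figures are right, but they show a limited gain and not a loss: a dose that fails the sequence stays exploratory, as every dose is now.

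Finally, a reader might infer that the sequence would answer the optimal-level question. It would not. That needs comparisons between active doses, which stay exploratory. The plan's rule of taking the largest point estimate does not answer it either: if all three doses have equal effects, it picks each about 33% of the time.

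**Conclusion.** The point holds in a limited form. A significant trend supports 90 mmol/day against placebo if the response is monotone, confirms nothing about 60 or 30 in any case, and confirms no particular dose if monotonicity is not granted. A fixed sequence would close most of this gap for 90 mmol/day (about 86% under the design values). At 60 (about 52%) it is close to a coin flip, and at 30 (about 15%) confirmation is unlikely. Failure to reject at those two doses would be weak evidence and must not be read as absence of effect.

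The primary test, its type I error and the sample size are sound, so this is a cheap improvement and not a defect in the primary analysis. The figures assume normal outcomes, an SD of 7 mm Hg in every arm, and 47 evaluable per arm (56 as the upper bound). They ignore the race covariate and the imputation. The non-monotone patterns are illustrations and do not come from the documents.

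**What to change.** Add one paragraph to 3I before unblinding:

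- If the linear contrast is significant at two-sided 0.05, test 24-hour systolic BP for 90 against 0, then 60 against 0, then 30 against 0 mmol/day, each two-sided at 0.05, stopping at the first non-significant result.
- Comparisons after the stop, and all comparisons between active doses, remain exploratory.
- Report all three net effects with confidence intervals whatever the test results, and state that non-significance at 60 or 30 mmol/day is not evidence of no effect.
- State that the sequence shows which doses differ from placebo and does not select an optimal dose.

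The cost is the paragraph itself, with no added participants, data or alpha and no change to the primary test. The downside is that a lower dose cannot be confirmed once a higher one fails, for example if the response peaks at 60 mmol/day.

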Study Participants	224 adults with elevated BP or hypertension (untreated office systolic/diastolic BP 120-159/<100 mm Hg)
Intervention Groups (n=56 per group)	Supplemental oral potassium in 3 arms: 30 mmol/day (1173 mg/day), 60 mmol/day (2346 mg/day), or 90 mmol/day (3519 mg/day) for 12 weeks
Control Group (n=56)	Placebo for 12 weeks
Primary Outcome	Difference in 24-hour systolic BP change from baseline to 12 weeks among the 4 groups
Secondary and other Outcomes	24-hour diastolic BP; office and nighttime BP; sodium excretion; effect mediation and modification by age, sex, race, baseline BP, central adiposity, baseline urine excretion of sodium and potassium, and change in urine sodium

3B. Randomization and Blinding

Eligible participants will be randomly assigned to placebo or 1 of 3 active intervention groups in a 1:1:1:1 ratio using a stratified (Black vs. non-Black) block (random sizes of 4 and 8) randomization scheme generated via computer program and concealed by an independent biostatistician within the Bioinformatics and Biostatistics Core. Randomization is expected to balance baseline characteristics (e.g., dietary intake) among groups. After eligibility is confirmed, clinical staff will ensure all baseline data is in place and checked for quality control purposes and will obtain the participant's randomization assignment via secure web-based database (REDCap). Once participants are randomized, every effort will be made to obtain complete follow-up information.

The proposed trial will employ placebo control and blinding of participants and study staff recording participant information, which are effective measures to account for the possibility of intervention placebo effects. The Bioinformatics and Biostatistics Core will control the randomization and intervention allocation, preserving the blinding of the investigators and Clinical Research and Community Engagement Core study staff in charge of day-to-day operations. Study participants will receive potassium tablets or placebo and will be unaware of their placebo or dosing assignment, and therefore unlikely to differentially change their diet over the course of the trial (i.e., cross-over). 24-hour BP monitoring is resistant to placebo effects and is unlikely to be affected by the possibility of observe unblinding.³³

3C. Intervention and Control

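### The primary change-score model leaves out baseline 24-hour systolic BP; the test is valid and adequately powered, but prespecifying that covariate would add precision at no cost

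*Combined protocol and SAP*

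**What the plan says.** Table 2 defines the primary outcome as "Difference in 24-hour systolic BP change from baseline to 12 weeks among the 4 groups". Section 3I tests it by linear regression with contrast coefficients -3, -1, 1, 3. Under Missing Data and Covariable Adjustment, the same section reasons that balance is expected and concludes that in the primary analysis "we will include the stratified randomization variable (i.e., race) as a covariable, but other covariable adjustments will not be used". Nothing elsewhere exempts the baseline value of the outcome; baseline BP otherwise appears only as a subgroup and effect-modification variable. Further adjustment is conditional and secondary: "if imbalances are detected, we will adjust for these covariables in secondary multivariable-adjusted regression models".

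Allocation (section 3B) is "in a 1:1:1:1 ratio using a stratified (Black vs. non-Black) block" randomization, so the design balances race but leaves baseline BP to chance. Section 3G sizes the trial on "a standard deviation of 7 mm Hg in 24-hour systolic BP change", which matches an analysis of change without baseline adjustment. Section 3D and the footnote to Table 3 require the baseline ambulatory recording to be checked for completeness before randomization.

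**The concern.** Expected balance is not a reason to leave out a prognostic baseline, because adjustment improves precision even when the arms are perfectly balanced. Nor does subtracting the baseline do the same job. If the baseline and week-12 values have equal SDs and correlation rho, a change score subtracts the whole of any baseline difference when only the fraction rho carries through to week 12. It over-corrects by (1 - rho) mm Hg for each mm Hg of imbalance.

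Two things are at stake: a wider confidence interval for the dose slope than the collected data allow, and a slope that moves with any chance baseline trend across the arms. The conditional adjustment in section 3I does not address either in the primary result. It sits in secondary models, and no threshold or covariate list says when or how it applies.

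**Working it through.** **Inputs from the documents.** Effect: "detect a 1.5 mm Hg reduction in 24-hour systolic BP for each additional 30 mmol/day", so the arm means are 0, -1.5, -3.0 and -4.5. SD of change: 7 mm Hg. Error rates: "90% statistical power; a 2-sided significance level of 0.05". Test: "The sample size calculation assumes analysis using a 4-group dose-response contrast test", with the coefficients from section 3I. Evaluable n: 47 per arm; recruited: 56 per arm, 224 in all (section 3G).

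**Input not in the documents.** The cross-sectional SD *s* of 24-hour systolic BP is assumed to be 9 to 12 mm Hg, equal at baseline and week 12. Any effect of race on the residual SD is ignored.

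**1. Reproduce the plan's figure.**
- Contrast: (-3)(0) + (-1)(-1.5) + (1)(-3.0) + (3)(-4.5) = -15. Sum of squared coefficients: 9 + 1 + 1 + 9 = 20.
- Standard error at 47 per arm: 7 × √(20/47) = 4.566. Noncentrality: 15/4.566 = 3.285.
- Two-sided t-based power: 90.5% at 47 per arm and 89.8% at 46, so 47 is the required number. Allowing for follow-up, 47/0.85 = 55.3, rounded up to 56; 4 × 56 = 224.

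The stated size reproduces for the unadjusted change-score contrast.

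**2. Precision from adding the baseline value.**
- SD of change = s√(2(1 - rho)) = 7, so rho = 1 - 49/(2s²).
- Residual variance after adjustment divided by change-score variance = (1 + rho)/2.
- Residual SD = 7√((1 + rho)/2).
- SE of the slope per 30 mmol/day = SD/√(5 × 47), since the contrast equals 10 times the slope. Unadjusted: 7/15.33 = 0.457.

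| Assumed s | rho | Variance ratio | Residual SD | Slope SE | Power, 47 per arm |
|---|---|---|---|---|---|
| Unadjusted | – | 1 | 7.00 | 0.457 | 90.5% |
| 9 | 0.70 | 0.85 | 6.45 | 0.421 | 94.4% |
| 10 | 0.755 | 0.88 | 6.56 | 0.428 | 93.7% |
| 12 | 0.83 | 0.915 | 6.70 | 0.437 | 92.7% |

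The gain is worth about 4 extra completers per arm at s = 12 (47/0.915 = 51.4) and about 8 at s = 9 (47/0.849 = 55.4). Outside this range, holding the SD of change at 7, power is about 97% if rho is 0.4 and about 92% if rho is 0.9.

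**3. Shift from a chance baseline trend.**
- One SE of the baseline slope is s/√(5 × 47). The unadjusted slope moves by (1 - rho) times that.
- s = 9: 0.3025 × 9/15.33 = 0.18 mm Hg per 30 mmol/day, or 12% of 1.5.
- s = 10: 0.245 × 10/15.33 = 0.16, or 11%.
- s = 12: 0.170 × 12/15.33 = 0.13, or 9%.
- For a comparison of two arms only, the shift is (1 - rho) × s × √(2/47): 0.56 mm Hg at s = 9 and 0.42 at s = 12.

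**4. Simulation** (4,000 trials at each of rho 0.4, 0.6 and 0.8; 47 per arm; SD of change 7).
- Mean slope was about -1.5 with or without adjustment.
- Per 1 mm Hg of baseline slope imbalance, the unadjusted slope moved by -0.58, -0.40 and -0.20, close to -(1 - rho). The adjusted slope moved by between -0.003 and 0.03.
- Power was 97.5%, 94.9% and 92.3% with adjustment, against about 90% without.

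**The case against.** The strongest reply is that nothing here is invalid. Under randomization the change-score contrast is unbiased, and chance baseline imbalance is part of the variability that the SD of 7 already carries, so the unadjusted standard error and p-value allow for it. The outcome definition, the sizing and the model are consistent with one another, and the trial meets its stated 90%. All of this stands.

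Three stronger readings are tempting and are not supported:

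- **The trial is underpowered.** It is sized for exactly the analysis it plans, and 47 per arm reproduces.
- **A typical chance imbalance distorts the primary result by about a third of a dose step.** A shift of 0.4 to 0.6 mm Hg set against 1.5 might suggest this, but that figure describes two arms. The primary test uses a four-arm slope, where the shift is 9% to 12% of target. The two-arm figure bears only on arm-by-arm comparisons, such as the section 3I definition of the optimal dose by net decrease against placebo.
- **The imbalance trigger makes the primary test data-driven.** Section 3I confines that adjustment to secondary models. Its undefined threshold is a weakness of those models alone.

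The size of the gain also rests on an SD the documents do not give, and it is small if rho is near 0.9. What survives is narrower: the primary model excludes a strong covariate that the protocol already collects, for a reason that does not justify excluding it.

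**Conclusion.** The point holds as a forgone gain in efficiency, not as an error that threatens the conclusion. The exclusion is clear from the text and does not depend on any assumption. Its size does: with a cross-sectional SD of 9 to 12 mm Hg, equal at both visits, the plan forgoes a 9% to 15% cut in residual variance and about 2 to 4 percentage points of power. It also leaves the slope open to a conditional shift of 0.13 to 0.18 mm Hg per 30 mmol/day for a one-standard-error baseline trend, which is 0.29 to 0.39 of the slope's unadjusted standard error. The direction is the same for any correlation below 1. This is a recommended improvement, not a must-fix.

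**What to change.** Before unblinding, amend section 3I to state that the primary linear-contrast model includes race and baseline 24-hour systolic BP as covariates whether or not imbalance is seen, and that each secondary BP outcome is adjusted for the baseline value of the same measure. The conditional multivariable models may remain as sensitivity analyses.

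The cost is a sentence or two. No new data are needed, because a complete baseline ambulatory recording is already a condition of randomization, and the sample size of 224 does not change. Timing matters: the same covariate added after unblinding would look like a post hoc choice.

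### The secondary adjusted model takes its covariates from an undefined look at baseline imbalance after randomization, so chance rather than prognostic value decides whether the model exists and what it contains

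*Combined protocol and SAP*

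**What the plan says.** Three statements in section 3I bear on this.

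- Under Preliminary Data Analysis, the baseline table has a purpose beyond description: "Intervention groups will be compared on baseline characteristics to identify possible baseline imbalances".
- Under Missing Data and Covariable Adjustment, the primary model is fixed in advance: "in the primary analysis, we will include the stratified randomization variable (i.e., race) as a covariable, but other covariable adjustments will not be used".
- The next sentence of that paragraph sets the rule for the adjusted model: "However, if imbalances are detected, we will adjust for these covariables in secondary multivariable-adjusted regression models".

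The plan does not say how the arms are to be compared, what counts as an imbalance, or which variables are candidates. The main test is a single-degree-of-freedom trend: "The linear contrast will be tested using contrast coefficients of -3, -1, 1, 3". Section 3I also limits the standing of everything outside that test: "The proposed trial is designed to test one primary hypothesis and the other analyses will be considered hypothesis generating".

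**The concern.** Section 3B describes a computer-generated allocation sequence, concealed by an independent biostatistician. Any baseline difference between arms is then due to chance. Adjustment is worthwhile when a covariate predicts the change in BP, and the observed imbalance of a variable says nothing about that. A rule based on imbalance can bring in irrelevant variables and leave out prognostic ones.

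The same section shows that the investigators can name variables they think relevant. Age, sex, race, baseline BP, central adiposity and baseline sodium and potassium intake are all listed for effect modification. Yet apart from race, none of them enters the adjusted main-effect model unless the draw happens to be uneven.

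Because no threshold is stated, what counts as imbalanced can be settled after the data are seen. At stake is the value of the adjusted estimate as a check on the primary one. It may not be produced at all. If it is produced, a reader cannot tell whether its covariates were fixed independently of the results.

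**Working it through.** **Inputs from section 3G.** Two-sided alpha 0.05 ("a 2-sided significance level of 0.05"), target power 90% ("90% statistical power"), SD 7 mm Hg ("a standard deviation of 7 mm Hg in 24-hour systolic BP change"), an effect of 1.5 mm Hg per 30 mmol/day, 47 evaluable per group, and 56 recruited per group at 85% follow-up. The contrast, from section 3I, is c = (-3, -1, 1, 3).

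**Step 1: reproduce the plan's own figure.** With net changes of 0, -1.5, -3.0 and -4.5, the sum of c² is 20 and the absolute value of the sum of c × μ is 15.

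- Normal approximation: n = (1.960 + 1.282)² × 7² × 20 / 15² = 45.8.
- Noncentral t with 4n - 4 degrees of freedom: power is 0.898 at n = 46 and 0.9045 at n = 47, so 47 per group is right.
- 47 / 0.85 = 55.3, which rounds up to 56 per group, 224 in total.

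The sample size reproduces. It does not depend on the adjusted model.

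**Step 2: how often chance would trigger the model.** Assume K independent variables, each tested at 0.05. The chance of at least one flag is 1 - 0.95^K.

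- K = 6 (the seven listed effect modifiers less race, which is stratified): 1 - 0.95⁶ = 26%.
- K = 15 (an assumed longer baseline table): 1 - 0.95¹⁵ = 54%.

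Correlation among the variables lowers the figure: for 15 variables in a simulation of 224 participants it was 42% at a pairwise correlation of 0.4.

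**Step 3: how well a screen lines up with the dose contrast.** Only the linear component of an imbalance can move the -3, -1, 1, 3 contrast. Under randomization, a four-group comparison splits into three independent components (linear, quadratic, cubic). Take imbalances that are significant at 0.05 in the linear direction, and ask what share a given screen fails to flag.

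| Screen (assumed; none is in the plan) | Share missed |
|---|---|
| Omnibus four-group test at 0.05 | 63% |
| Omnibus test at 0.10 | 37% |
| Placebo vs 90 mmol/day only, at 0.05 | 29% |
| Any of six pairwise tests at 0.05 | 9% |
| Omnibus test at 0.20 | 7% |
| Any pairwise standardized difference above 0.25 | 0% |

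The first row comes from chi-square integration (62.8%). Simulation with finite degrees of freedom gave 62.5% at both 47 and 56 per group. The last rule misses nothing, but it flags about 55% of variables by chance.

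**Step 4: what a fixed set would give.** If the covariates explain a share R² of the variance in change, the residual SD is 7 × √(1 - R²). At 47 per group, ignoring the few degrees of freedom spent:

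- R² = 0: SD 7.00, power 90.5%.
- R² = 0.05 (assumed): SD 6.82, power 91.8%.
- R² = 0.10 (assumed): SD 6.64, power 93.1%.

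**The case against.** The strongest reply is about weight. The primary model is fixed in advance with race as its only covariate. The adjusted models are called secondary, and all analyses beyond the primary hypothesis are labelled hypothesis generating. This stands: the primary estimate, its alpha and the sample size are untouched.

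A second reply concerns the 63%. A reader might infer that the plan's own check misses that share of the relevant imbalances. The documents do not support this, because they name no test, alpha or threshold, and the comparison may be no more than an inspection of summary statistics. Even under the omnibus assumption the figure needs context. A significant linear imbalance has 5% probability per variable, so significant and missed is about 0.05 × 0.63 = 3% per variable. In the large-sample limit, any linear z above √7.815 = 2.80 is always flagged. It would therefore be too strong to say that the check gives no reliable protection. Nor does the case for the change need the number: a screen that caught every imbalance would still ignore prognostic value.

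A third reply is that covariates are examined elsewhere. Section 3I plans stratified and interaction analyses for the listed modifiers whatever the balance. That is true, and it rules out saying that covariates are otherwise neglected. But those analyses ask whether the effect differs between subgroups; they do not give an adjusted overall slope.

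**Conclusion.** The point holds as a modest one about a secondary analysis. The plan does state a selection rule, and it is a poor one. It leaves both the existence and the content of the adjusted model to the draw, and prognostic value has no say.

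This conclusion needs only the wording of section 3I and valid concealed randomization. The figures are illustrations. The 26% to 54% assumes 6 to 15 independent variables tested at 0.05. The miss rate runs from 0% to 63% according to which unstated rule is used, and that spread shows how much is left undefined. The gain from 90.5% to about 92% to 93% power rests on an assumed R² of 0.05 to 0.10 and applies to the secondary model only. None of this supports a claim that the primary analysis is biased or that the trial is underpowered.

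**What to change.** Delete the sentence that makes adjustment depend on detected imbalance. Replace it with one secondary adjusted model, fixed before unblinding and reported whatever the baseline table shows. Its covariates would be the race stratum, the baseline value of the BP outcome being analysed, age, sex, waist circumference, and baseline 24-hour urinary sodium and potassium. Baseline BP belongs in the list because the outcome is a change from that value.

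Keep the comparison of arms at baseline as description, and state that it has no role in choosing covariates.

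The cost is SAP wording. Every variable is already collected under sections 3D and 3E. Beyond race, the list adds six terms, so it uses about six of the 4 × 47 - 4 = 184 degrees of freedom. The primary analysis does not change.
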